10 WITHDRAWAL CRITERIA

Patients are free to discontinue the trial at any time without giving their reasons without losing the right to future medical care. Patients who withdraw from the trial will also be withdrawn from the investigational medicinal product.

Patients who voluntarily withdraw their consent can do so for any of the following reasons:

- Does not want to participate in the study anymore
- Does not permit further collection of personal data

The investigator should make a reasonable effort to understand the primary reason for the patient's decision to withdraw his/her consent and record this information.

Study participants may, at any moment, be withdrawn by the Investigator, if considered appropriate. Patients can be withdrawn for any of, but not limited to, the following reasons:

- If the patient meets an exclusion criterion (newly developed or not previously recognized) that precludes further study participation
- Adverse events: when during the conduct of the study, adverse events occur
 that, in the Investigator's judgement, are of such a nature or severity to
 recommend treatment withdrawal
- Failure to comply with requirements of the protocol including, but not limited to evidence of non-compliance with inclusion/exclusion criteria during the study or patient non-compliance with key study procedures

МЕМАЯНИ	Согр	porate Medical Departmo	ent
Identification Number	Version Number	State	Effective date
FORM-000050125	2.0, CURRENT	Effective	08, Jan 2021

- By request of the patient including explicit withdrawal of patient's consent to participate
- Patient's failure to report to study visits
- Patient's loss to follow-up (for guidance see Section 11)
- Withdrawal by Investigator's judgement: Investigator may choose to withdraw a patient from the study if the Investigator deems it in the best interest of the patient to discontinue.

Patients who satisfy the following criteria will also be withdrawn from the study:

- If at Visit 2 patients have a controlled BP (sitting SBP/DBP ≤130/80 mmHg) or do not tolerate the treatment or have an adherence range below 80% or superior to 120%.
- If at Visit 3 the patients do not tolerate the extemporaneous combination treatment or have an adherence range below 80% or superior to 120%.
- Patients with abnormal renal function (creatinine clearance <30 mL/min) and/or abnormal liver enzyme parameters (alanine aminotransferase [ALT] or aspartate aminotransferase [AST] level of >2.5 × upper limit of normal [ULN] or total bilirubin level >1.5 × ULN).

If a patient has been withdrawn due to an AE, the Investigator must immediately contact the relevant pharmacovigilance contact (see Safety Data Management section). The reason for patient withdrawal must be well-documented in the Electronic Case Report Form (eCRF). The eCRF should capture the date and specific underlying reason for discontinuation of study product or patient discontinuation/withdrawal. Study treatment must be discontinued, and no further assessment conducted, and the data that would have been collected at subsequent visit will be considered missing. Further attempts to contact the patient are not allowed unless safety findings require communication or follow-up. All effort should be made to complete the assessment prior to study withdrawal. A final evaluation at the time of the patient's study withdrawal should be made as detailed in Early termination visit scheduled assessment.

Patients who discontinue from the study early will complete an early termination visit.

MENARINI	Corporate Medical Department		
	** * ** *	G	77.00 dt 1
Identification Number	Version Number	State	Effective date
FORM-000050125	2.0, CURRENT	Effective	08, Jan 2021

Subjects who prematurely withdrawn from study medication or from the study will not be replaced. These subjects will not be considered lost to follow-up.

11 LOST TO FOLLOW UP

A patient will be considered lost to follow-up if he or she fails to return for 2 or more scheduled visits and is unable to be contacted by the study site staff.

The following actions must be taken if a patient fails to return to the clinic for a required study visit.

The site staff will attempt to contact the patient and reschedule the missed visit within 2 business days. Site staff will counsel the patient on the importance of maintaining the assigned visit schedule and ascertain if the patient wishes to and/or should continue in the study.

Before a patient is deemed lost to follow-up, the investigator or designee will make every effort (e.g. letters, telephone calls) to regain contact with the patient. Each contact attempt should be documented in the patient's medical record or study file.

12 STATISTIC

This section outlines the major features of statistical analyses. More detailed methodology for summary and statistical analysis of data collected in this study will be documented in the statistical analysis plan (SAP), which will be maintained by the sponsor and completed prior to locking the database. The SAP may modify the plans outlined in the protocol; however, any major modifications of the primary endpoint definition and/or its analysis will also be reflected in a protocol amendment.

Any additional or supplemental data analyses performed independently by the investigator should be submitted to the Sponsor.

12.1 Statistical Methods (Blinding and Randomization)

This is a non-randomized, unblinded study. Unless specified otherwise, all statistical testing will be two-sided and will be performed using a significance (alpha) level of 0.05.

MENARINI	Corporate Medical Department		ent
Identification Number	Version Number	State	Effective date
FORM-000050125	2.0, CURRENT	Effective	08, Jan 2021

Sponsor: Menarini International Operations Luxembourg SA Study Code: MEIN/20/ZoAm-Hyp/001	Protocol Version 1.0 of 1	23/04/2021

12.2 Determination of Sample Size

A total sample size of 216 patients is required to achieve 90% power at a 5% significance level assuming a difference in mean DBP from baseline (Visit 2) to 8 weeks (Visit 4) of 4 mmHg and a standard deviation (SD) for this difference of 10 mmHg. The mean change in DBP for the null hypothesis is set equal to 2 mmHg. To achieve this, a total of 290 patients will be enrolled, allowing for a 25% withdrawal rate.

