5 STUDY DESIGN

This is a phase IV, open-label, multicentre, multinational study with 2 study periods: a 4-week run-in period and an 8-week assessment period.

Approximately 290 patients are planned to be screened to ensure at least 216 patients complete the run-in period and start with the assessment period.

Patients with Grade 1-2 hypertensive patients (blood pressure [BP] ranging from ≥140/90 mmHg to ≤179/109 mmHg) on treatment with any angiotensin converting enzyme inhibitors (ACE-i) including Zofenopril 30 mg or with calcium channel blockers (CCBs) including Amlodipine 5 mg will be screened for eligibility (Visit 1).

Allowed CCBs: Felodipine, isradipine, lacidipine, lercanidipine, nicardipine, nifedipine, and nisoldipine. Patients treated with other dosages of Zofenopril (other than 30 mg) are not allowed to be screened.

After screening, on the same day, eligible patients, will enter into a 4-week run-in period, during which patients on other ACE-i will be assigned to monotherapy with ZOF 30 mg while patients on CCBs[§] will be assigned to monotherapy with AML 5 mg for 4 weeks. Patients with on-going treatment zofenopril 30 mg and amlodipine 5mg will continue on the same treatment for 4 weeks.

After the run-in period (4 weeks \pm 2 days), BP will be further assessed (Visit 2), if BP levels are over the defined controlled target goal (sitting SBP/DBP >130/80 mmHg), treatment is well tolerated and adherence to the treatments ranges from 80% to 120%, patients will enter the assessment period, where they will be assigned to the extemporaneous combination of ZOF 30 mg and AML 5 mg. At Visit 2 patients with SBP/DBP values classified as Grade 3 (SBP \geq 180 or DBP \geq 110 mmHg) hypertension will be withdrawn from the study.

If patients, at Visit 2, after the run-in period, have a controlled BP (sitting SBP/DBP≤130/80 mmHg) or do not tolerate the treatment or have an adherence range below 80% or superior to 120%, they will be withdrawn from the study.

The patients will be assessed for further 8 weeks (assessment period).

After 4 weeks \pm 2 days from Visit 2, during the assessment period patients receiving the extemporaneous combination of ZOF 30 mg and AML 5 mg, will be further evaluated (Visit 3): controlled patients (sitting SBP/DBP \leq 130/80 mmHg) will continue the same

MENARINI	Corporate Medical Department		
Identification Number	Version Number	State	Effective date
FORM-000050125	2.0, CURRENT	Effective	08, Jan 2021

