Identification Number	Version Number	State	Effective date
FORM-000050125	2.0, CURRENT	Effective	08, Jan 2021

- Study Drug Compliance assessment by return of monotherapy ZOF and AML tablets (also empty blister) and IP accountability
- AEs and serious adverse events (SAEs) assessment
- IWRS update
- Patient's instruction to use the automatic blood pressure device, including patient's diary to be returned at site by the patient

The patients with uncontrolled BP (SBP/DBP >130/80 mmHg), who tolerated the treatment and whose adherence to the therapy ranges from 80% to 120%, will enter the assessment period and at this visit will be dispensed with extemporaneous combination of ZOF 30 mg and AML 5 mg.

To correctly evaluate the additional effect of the combination therapy, the number of patients with uncontrolled BP on AML or ZOF monotherapy needs to be balanced at Visit 2. In order to maintain a 1:1 ratio during the assessment period, a cap of 110 patients for each arm (i.e., AML and ZOF) will be included at Visit 2 in order to maintain a balanced number of uncontrolled patients entering the assessment period for each drug (please refer to section 8 IWRS registration). The evaluation will be done every 50 patients. If the rate of entrance in the assessment period for one of the 2 tested drugs will deviate more than 5%, a corrective measure will be initiated: according to the enrolment site statistics, one or more sites will be informed to enrol a greater number of patients being treated with the least represented drug in the assessment period.

Visit 3 (Week 4 ± 2 days)

The following procedures/assessments will be performed at Visit 3:

- Recording of concurrent diseases and medical conditions
- Concomitant medications
- Vital sign measurements
- Physical Examinations
- BP Measurement
- Urine pregnancy test (UPT)
- Study Drug Compliance assessment (Study Drug Compliance assessment extemporaneous combination of ZOF 30 mg and AML 5 mg) return (also empty blisters) and IP accountability

ИЕМАЯНИ	Corporate Medical Department		
Identification Number	Version Number	State	Effective date
FORM-000050125	2.0, CURRENT	Effective	08, Jan 2021

- AEs and serious adverse events (SAEs) assessment
- IWRS updates
- Patient's instruction to use the automatic blood pressure device, including patient's diary to be returned at site by the patient

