6 SELECTION OF SUBJECTS

The following subject will be screened:

- Male or female, (Grade 1-2), uncontrolled hypertensive patients ≥18 and ≤65 years of age
- Considering a screening failure and a drop-out rate of 25%, the overall number of patients to be screened is 290.
- 216 patients needed to complete the run-in period and enter the assessment period to guarantee powered results

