### 4.6 Sample Size

A total sample size of 216 patients is required to achieve 90% power at a 5% significance level

assuming a difference in mean DBP from baseline (Visit 2) to 8 weeks (Visit 4) of 4 mmHg and a standard deviation (SD) for this difference of 10 mmHg. The mean change in DBP for the null hypothesis is set equal to 2 mmHg. The alternative hypothesis is that the mean change in DBP is greater than 2 mmHg. To achieve this sample size, a total of 290 patients will be enrolled, allowing for a 25% withdrawal rate.

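### The single 25% allowance is used up by Visit 2, so the 90% power stated against the 2 mmHg null has no margin for loss between Visit 2 and Visit 4

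*Protocol*

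**What the plan says.** The power statement in Protocol 12.2 concerns a within-patient change. "A total sample size of 216 patients is required to achieve 90% power at a 5% significance level", and the calculation proceeds "assuming a difference in mean DBP from baseline (Visit 2) to 8 weeks (Visit 4) of 4 mmHg", with an SD of 10 mmHg and a null mean change of 2 mmHg. The 216 is thus a number of patients with both a Visit 2 and a Visit 4 value. The inflation follows directly: "To achieve this, a total of 290 patients will be enrolled, allowing for a 25% withdrawal rate". SAP 4.6 has the same sentence in substance ("a total of 290 patients will be enrolled, allowing for a 25% withdrawal rate") and adds that the alternative is a change greater than 2 mmHg.

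Other sections count 216 at an earlier point. Protocol 5 says: "Approximately 290 patients are planned to be screened to ensure at least 216 patients complete the run-in period and start with the assessment period". The synopsis, Protocol 5.1 and SAP 4.1 agree. Protocol 6 says what the 25% covers: "Considering a screening failure and a drop-out rate of 25%, the overall number of patients to be screened is 290". The synopsis and Protocol 6 also present 216 entrants as the number that guarantees a powered result.

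Three provisions act after that point:

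- Protocol 5 and 10 withdraw patients at Visit 3 for Grade 3 blood pressure, intolerance, or adherence outside 80% to 120%.
- Protocol 10 rules out making up the numbers: "Subjects who prematurely withdrawn from study medication or from the study will not be replaced".
- Protocol 5.1 limits entry: "a cap of 110 patients for each arm (i.e., AML and ZOF) will be included at Visit 2".

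**The concern.** One allowance is described in two ways. In Protocol 12.2 and SAP 4.6 it is a withdrawal rate that protects the 216 needed for the Visit 4 comparison. Elsewhere it takes 290 screened patients to 216 starting the combination. It cannot do both. On the second reading, which most sections give, nothing is set aside for loss over the 8 weeks in which the primary endpoint is observed.

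The term attached to 290 also changes, from screened to enrolled. The two differ in this protocol: under 6.2.3, screening failures never enter the run-in.

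Missing Visit 4 values reduce the primary analysis directly. Protocol 12.3 includes patients only where they have data. SAP 5.3.3 admits patients to the Efficacy Population on a Visit 3 value alone. SAP 5.6.1 confines LOCF to the sensitivity analysis. What is at stake is whether the quoted 90% describes the number of pairs the trial is set up to yield.

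**Working it through.** **Inputs from the documents.** Mean change 4 mmHg, null 2 mmHg, SD 10 mmHg, alpha 5% (Protocol 12.2, SAP 4.6). Alternative greater than 2 mmHg (SAP 4.6). Testing two-sided unless stated otherwise (Protocol 12.1). Primary test against 0 mmHg, two-sided (Protocol 12.5.2, SAP 7.2.1). Allowance 25%, and 290 screened or enrolled. Cap of 110 per monotherapy (Protocol 5.1).

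**Assumption.** The documents give no loss rate between Visit 2 and Visit 4. A range of 5% to 25% is used.

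**1. Reproduce 216.** For a paired t-test, n is approximately (SD x (z_alpha + z_power) / difference)^2, with difference = 4 - 2 = 2.

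- One-sided 5%: (10 x (1.645 + 1.282) / 2)^2 = 214.1. The noncentral t gives 216, with power 90.07% at 216 and 89.95% at 215.
- Two-sided 5%: (10 x (1.960 + 1.282) / 2)^2 = 262.7. The noncentral t gives 265, with power 83.3% at 216.

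So 216 reproduces exactly as a one-sided calculation, and it is the smallest number of pairs that reaches 90%.

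**2. Reproduce 290.** 216 / 0.75 = 288, and 290 x 0.75 = 217.5. The 290 is consistent with one 25% loss and 216 remaining. By the synopsis, Protocol 5, 5.1 and 6 and SAP 4.1, that loss has occurred by entry to the assessment period.

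**3. Margin after Visit 2.** The cap gives 2 x 110 = 220 entrants. Keeping 216 pairs allows 220 - 216 = 4 losses, and 4 / 220 = 1.8%. With exactly 216 entering, no loss is allowed.

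**4. Power with 216 entering.** Pairs = 216 x (1 - loss), rounded down; power by noncentral t.

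| Assumed loss after Visit 2 | Pairs | Null 2 mmHg, one-sided | Null 2 mmHg, two-sided | Null 0 mmHg, two-sided (planned test) |
|---|---|---|---|---|
| 0% | 216 | 90.1% | 83.3% | 99.995% |
| 5% | 205 | 88.7% | 81.3% | 99.99% |
| 10% | 194 | 87.1% | 79.2% | 99.98% |
| 15% | 183 | 85.3% | 76.8% | 99.97% |
| 20% | 172 | 83.3% | 74.2% | 99.94% |
| 25% | 162 | 81.3% | 71.6% | 99.90% |

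With 220 entering and 10% loss, 198 pairs remain: 87.7% one-sided and 80.0% two-sided against 2 mmHg.

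**5. Entrants needed to keep 216 pairs.** 216 / (1 - loss), rounded up, gives 228 at 5%, 240 at 10%, 255 at 15%, 270 at 20% and 288 at 25%. Each exceeds 220.

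**The case against.** The strongest reply is that the shortfall concerns a test nobody will run. The planned primary test is two-sided against 0 mmHg. On the plan's own mean and SD it has 99.90% power with 162 pairs, and 68 pairs would give 90%. This stands. A reader might infer that the primary analysis is underpowered; under the stated assumptions it is not.

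A reader might also infer that the design cannot yield 216 pairs. The documents do not support that either. With 220 entrants and no more than 4 losses, 216 pairs remain, and Protocol 5 sets 216 as a minimum. The absolute cap appears only in Protocol 5.1; Protocol 8 caps each monotherapy at 50% instead. The size of the deficit rests on an assumed rate, and one-sided power is still at least 88% with 201 pairs, a loss of about 7% from 216.

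Nor is there a miscalculation: 216 and 290 both reproduce. The fault is in what the figures denote.

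Withdrawal need not mean a lost final reading. Protocol 2.2 asks for the Visit 4 assessments when a patient stops early, Protocol 10 requires a termination visit, and SAP 5.2.4 puts such visits in the summary tables. But Protocol 10 also treats data from later visits as missing, SAP 5.2.4 tabulates by the visit recorded, and neither document says that a termination reading counts as Visit 4. The question is open.

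Finally, the conflict over the null (2 or 0 mmHg) and sidedness is larger: with all 216 pairs, two-sided power against 2 mmHg is 83.3%. That is a separate problem. Settling it at 0 mmHg makes the shortfall here immaterial; settling it at 2 mmHg leaves the shortfall in place.

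**Conclusion.** The accounting point holds. The 216 needed as Visit 2 to Visit 4 pairs is counted at entry to the assessment period, and the 25% is exhausted by then. No allowance is stated for later loss, although the protocol provides for withdrawal at Visit 3, rules out replacement and caps entry at 220. Since 216 is the exact minimum, the stated 90% is not secured for the 2 mmHg sizing null.

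The shortfall is modest on the one-sided sizing hypothesis: about 1 point at 5% loss, 3 points at 10% and 9 points at 25%. It depends on an assumed loss rate and on early-termination readings not counting as Visit 4. It does not touch the planned test against 0 mmHg.

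**What to change.** In the synopsis, Protocol 12.2 and SAP 4.6:

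- say that 216 is the number entering the assessment period;
- describe 290 as screened throughout;
- give the loss before Visit 2 (25%) and an assumed loss from Visit 2 to Visit 4 as separate figures;
- state the expected number of pairs and the power at that number, naming the null and the sidedness. Do this once the 2 versus 0 mmHg and one- versus two-sided conflict is reconciled. A bare figure such as 87% would be misleading, because at 10% loss it is the one-sided value against 2 mmHg, the two-sided value is 79.2%, and the planned test is against 0 mmHg.

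In the SAP, also state whether an early-termination blood pressure counts as the Visit 4 value in the primary analysis.

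The cost is wording and, if the 2 mmHg null is kept, a slightly less favourable power figure. No extra patients are needed if the power is restated. If the sponsor wants to keep 90% against 2 mmHg, then 216, 290 and the cap must be revised together. At 10% later loss, the one-sided calculation needs 240 entrants and, at the same 25% earlier loss, 240 / 0.75 = 320 screened.

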12.3 Analysis Populations

A total of three populations will be used for all summaries and analyses. Study participants who have satisfied the population criteria will be classified in the designated population and will only be included in analyses for which they have available data.

Data analysis will be performed using the following analysis sets.

The Safety Population

The Safety population is defined as all study participants who sign the informed consent, meet all screening criteria, are enrolled, and receive at least one dose of the assigned treatment during the run-in period. This population will be used for safety analyses.

The Efficacy Population

The Efficacy population is defined as all study participants in the Safety population who complete the 4-week run-in period and the Visit 2 blood pressure assessment. This will be population for efficacy analysis.

The Per-Protocol Population

The Per-Protocol (PP) population is defined as all study participants in the Efficacy population who were dosed according to protocol, complete the required study visits, and do not experience any major protocol deviations that may impact the primary efficacy assessment through end of treatment.

HEVARIN	Corporate Medical Department		
Identification Number	Version Number	State	Effective date
FORM-000050125	2.0, CURRENT	Effective	08, Jan 2021

12.4 Analysis Variables

The primary endpoint (i.e. change in sitting Diastolic Blood Pressure from Visit 2 to Visit 4) and primary statistical analysis specifications will be detailed in 12.5.2. Secondary endpoints and their respective statistical analyses are summarized in 12.5.4 while safety analyses in 12.5.7. Data handling and imputation methods are reported in 12.5.9.

12.5 Statistical Analysis

12.5.1 Descriptive statistics

Descriptive statistics for categorical variables (such as gender, race, and ethnicity) will include the number and percent of study participants with each characteristic. Percentages will be based on the number of study participants with non-missing values. Descriptive statistics for ordinal and continuous variables will include the number of study participants with non-missing values, mean, median, standard deviation, minimum value, and maximum value. Intervals representing 95% confidence will be presented when appropriate. Graphical displays will be present when appropriate.

All relevant data collected in the eCRF will be shown for each study participant in the individual study participant data listings.

Disposition

A tabulation of the disposition of study participants will be presented, including the number enrolled, the number treated, and the reasons for study discontinuation. Summaries of the number in each analysis set will be presented. Entry criteria violations and protocol deviations will be listed.

Demographics and Baseline

Demographic and baseline characteristic data summarization will be performed. Data to be tabulated will include study site, gender, age, race, and ethnicity, as well as baseline characteristics related to medical history.

12.5.2 Primary (efficacy) analysis

For the primary efficacy analysis of the primary endpoint, the change in sitting Diastolic Blood Pressure (DBP) from Visit 2 to Visit 4 will be assessed using a paired t-test. A Type I error

MENARINI	Corporate Medical Department		
Identification Number	Version Number	State	Effective date
FORM-000050125	2.0, CURRENT	Effective	08, Jan 2021

Sponsor: Menarini International Operations Luxembourg SA Study Code: MEIN/20/ZoAm-Hyp/001	Protocol Version 1.0 of 1	23/04/2021

threshold of 0.05 will be used to test the null hypothesis that the mean reduction in DBP is 0 mmHg against a two-sided alternative. The Efficacy population will be used to analyse the primary endpoint.

